#### **3.2. Endpoints**

##### **3.2.1. Effectiveness**

There are two co-primary effectiveness endpoints:

- Percent change in total body weight (%TBL) at 32 weeks; and
- Clinical response, where a responder is defined as a subject with at least a 5% loss in total body weight at 32 weeks

There are two secondary endpoints:

- Maintenance of 40% of the total body weight loss with the balloon six months after the balloon is removed
- Clinical response, where a responder is defined as a subject with at least a 25% loss in excess body weight at 32 weeks

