#### 7.1.2. Primary Endpoints

The co-primary hypotheses are as follows:

1. The mean %TBL in the Spatz3 group exceeds that in the control group by 4.5%. In formal terms, this is:

$$H_0: \mu_S - \mu_C \leq 4.5\%$$

vs.

$$H_A: \mu_S - \mu_C > 4.5\%,$$

where  $\mu_S$  and  $\mu_C$  are the population mean %TBL for the Spatz3 and control groups, respectively.

2. The response rate in the Spatz3 group is superior to a performance goal of 50%, where a responder is defined as a  $\geq 5\%$  loss in total body weight at 32 weeks. In formal terms, this is:

$$H_0: \pi \leq 50\%$$

vs.

$$H_A: \pi > 50\%,$$

where  $\pi$  is the population response rate in the Spatz3 group.

All missing body weight data will first be imputed as follows. Initially, all interim missing data (missing data for which there is at least one subsequent non-missing body weight) will be linearly interpolated based on the last and subsequent non-missing body weight. If a subject in the Spatz3 group has the balloon explanted, the body weight immediately preceding the explant will be used and the subject will be treated as a dropout from that time forward, even though the subject will be followed for another 24 weeks. After the interim missing data have been interpolated, all additional missing data will be imputed using a regression method for multiple imputation. Baseline body weight, baseline BMI, subject's gender, study center, treatment group, and all non-missing body weight measurements through Week 32 will be included in the imputation model. A total of five imputed datasets will be created. The first primary endpoint, %TBL at 32 weeks, will be analyzed by an analysis of covariance that includes the effects of treatment group, study center, baseline BMI group ( $< 35 \text{ kg/m}^2$  vs.  $\geq 35 \text{ kg/m}^2$ ) and subject's gender as covariates. The parameter estimates from the five imputations

will be used to estimate a one-sided lower 97.5% confidence bound on the difference in mean %TBL (Spatz3 mean minus control mean). If this lower confidence bound exceeds the super-superiority margin of 4.5% the Spatz3 will be deemed to have super-superiority over the control group in %TBL.

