### **7.1.3. Secondary endpoints**

The observed rate of subjects who maintain 40% of the weight loss with the balloon at six months will be compared to a performance goal of 50%.

Percent change in excess weight loss (%EWL) will be calculated by first calculating the excess weight based on a BMI of  $25 \text{ kg/m}^2$ . This endpoint will be analyzed by averaging the mean 32-week changes in body weight for each subject across the five imputations described for the primary endpoint to determine which subjects had a clinical response of a  $\geq 25\%$  loss in excess body weight. This response rate will be compared to a performance goal of 35%.

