#### **7.1.5. Missing data**

Missing data will be imputed as described above in [Section 7.1.2](#).

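### The six-month maintenance endpoint has no stated denominator, bound, no-loss class or workable missing-data rule; its natural reading is a completers-only rate that could meet the 50% goal too easily

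*Combined protocol and SAP*

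**What the plan says.** All references are to the combined protocol and SAP.

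- **Endpoint (3.2.1):** "Maintenance of 40% of the total body weight loss with the balloon six months after the balloon is removed".
- **Analysis (7.1.3), one sentence:** "The observed rate of subjects who maintain 40% of the weight loss with the balloon at six months will be compared". The comparator is a fixed goal, 50%. No analysis set, denominator, test, bound, alpha or missing-data rule is named.
- **The other secondary endpoint (7.1.3), 25% excess weight loss:** responders are found by averaging "across the five imputations described for the primary endpoint to determine which subjects had a clinical response". Imputation is named there and not for maintenance.
- **General rule (7.1.5):** "Missing data will be imputed as described above", meaning as in 7.1.2.
- **Imputation (7.1.2):** it opens broadly, "All missing body weight data will first be imputed as follows", but its stated inputs end at Week 32: "all non-missing body weight measurements through Week 32 will be included in the imputation model". After explant, "the subject will be treated as a dropout from that time forward, even though the subject will be followed for another 24 weeks".
- **Analysis set (7.1.1):** intent-to-treat is named for the primary analysis. Subjects not implanted because of an absolute contraindication found at endoscopy are left out of the efficacy analysis.
- **Sensitivity analysis (7.1.2):** LOCF is specified for the co-primary endpoints only.
- **Follow-up (4.3.4):** treatment subjects are weighed through Week 56, or through 24 weeks after an early extraction. Controls exit at Week 32.

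**The concern.** Three choices that determine the result are left open.

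1. **Who is counted.** If the rate covers only subjects weighed six months after removal, and those not weighed maintain less often, it is biased upward. Controls have left by then, so no concurrent arm could reveal the bias.
2. **How a missing weight is handled.** The cross-reference leads to a procedure built for Week 32. Its dropout-at-explant rule would discard the very data that define maintenance.
3. **How a subject with no loss, or a gain, on the balloon is classed.** For such a subject 40% of the loss is zero or negative, so the criterion has no sensible meaning. Depending on coding, the subject could be a failure, an exclusion or a success.

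At stake is the plan's only prespecified durability endpoint, one of two secondary endpoints. If nothing changes, these choices could be settled after the data are seen.

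**Working it through.** **The plan's own figure (7.2).** Inputs: means 10.34% and 3.3%, margin 4.5%, SD 6.6%, 160 and 80 subjects, one-sided 2.5%.

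- Difference beyond the margin: 10.34 − 3.3 − 4.5 = 2.54.
- SE = 6.6 × √(1/160 + 1/80) = 0.904.
- Power = Φ(2.54/0.904 − 1.96) = Φ(0.85) = 80.2%.
- Dropout: 240/0.85 = 282.4, against 282 stated.

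Both figures reproduce. The plan gives no sample size or power for the maintenance endpoint.

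**Assumptions for the illustration.** None of these is stated for this endpoint: 15% missing (the allowance in 7.2), 188 as the full denominator, and a one-sided 97.5% exact lower bound that must exceed 50%. Observed subjects: 188 × 0.85 ≈ 160.

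**Passing thresholds.**

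| Denominator | Fewest maintainers to pass | Rate | Exact lower bound | Share of 188 |
|---|---|---|---|---|
| 188 (all) | 108 | 57.4% | 0.500 (just above) | 57.4% |
| 160 (completers) | 93 | 58.1% | 0.501 | 49.5% |

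A completers-only pass at 93/160 therefore shows maintenance in less than half of the arm.

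**Chance of passing when the true all-subject rate is 50%.** If a fraction *f* of the missing maintain, the completers' rate is (0.50 − 0.15*f*)/0.85. The chance of passing is P(X ≥ 93) for a binomial with n = 160 at that rate.

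| *f* | Completers' rate | P(pass) |
|---|---|---|
| 0% | 58.8% | 60% |
| 10% | 57.1% | 43% |
| 25% | 54.4% | 19% |
| 40% | 51.8% | 6% |

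With all 188 counted, P(X ≥ 108) at 50% is 2.4%. With 5% missing (179 observed, threshold 104) and *f* = 0, the completers' rate is 0.50/0.95 = 52.6% and P(pass) is about 8%.

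**Subjects with no loss.** Using the planning mean and SD and assuming normality, Φ(−10.34/6.6) = Φ(−1.57) = 5.9%. That is about 11 of 188, or 9 of 160. Take 160 observed, of whom 9 had no loss and 89 of the others maintained:

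| Class of the 9 | Rate | Exact lower bound | Result |
|---|---|---|---|
| Not maintained | 89/160 = 55.6% | 0.476 | fails |
| Excluded | 89/151 = 58.9% | 0.507 | passes |
| Maintained | 98/160 = 61.3% | 0.532 | passes |

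The classification alone can change the outcome. When missing and no-loss subjects are both left out, the passing 89 are 89/188 = 47.3% of the arm.

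**The case against.** The strongest reply is that this is silence and not a biased rule. An observed rate may simply mean the sample proportion set against a fixed goal. Section 7.1.5 is not limited to primary endpoints, and 7.1.2 opens by covering all missing weights. A regression model with inputs through Week 32 could in principle predict a later weight. The dropout-at-explant rule was evidently written for the Week 32 endpoint.

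Part of this stands, and it rules out several stronger readings that a reader might infer:

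- **That the plan adopts a completers-only analysis.** It does not say so. The contrast with the neighbouring endpoint makes this the natural reading and no more.
- **That the imputation model cannot yield a value six months after removal.** The supported problem is narrower: the plan describes no such extension, and the explant rule, read literally, discards the relevant weights.
- **That the decision rule is looser than the co-primary rule.** No rule is given. If a point estimate above 50% were enough, a true 50% rate would pass about 47% of the time with 160 observed, but that rule is an assumption.
- **That late visits will be missed by those who regain.** This is plausible, but the documents do not show it.
- **That this is the only evidence on durability.** Weights are scheduled across Weeks 36 to 56. It is only the sole prespecified durability endpoint.

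The size is also conditional. The 15% comes from a 32-week sample-size calculation, and 188 is everyone randomized to Spatz3, so the implanted number may be smaller. The no-loss estimate borrows another device's six-month SD.

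The reply does not remove the gap. Sections 7.1.3, 7.1.5 and 7.1.2 together still give no usable rule for this endpoint, and nothing in them classes a subject without loss.

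**Conclusion.** The point holds as under-specification with a material consequence. Followed as written, the sections lead either to a completers-only rate or to setting aside the post-removal weights.

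Under the stated assumptions, a true 50% rate would pass between about 6% and 60% of the time at 15% missing, against a nominal 2.5%. The bias is upward only if missing subjects maintain less often than observed ones, and it is modest when few are missing. The no-loss gap does not depend on missing data: about 11 of 188 subjects are affected under the planning values, enough to reverse a result near the threshold.

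This is a secondary endpoint. It should be settled before the six-month post-removal data are analysed.

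**What to change.** Amend 7.1.3, with a matching line in 7.1.5:

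- **Denominator:** all implanted Spatz3 subjects, consistent with the exclusion in 7.1.1.
- **No net loss at extraction:** counted as not maintained.
- **Missing six-month weight:** extend the imputation model through 24 weeks after extraction, using the post-extraction weights. State that the dropout-at-explant rule in 7.1.2 does not apply to this endpoint.
- **Decision rule:** the one-sided 97.5% lower bound must exceed 50%, as for the second co-primary endpoint.
- **Sensitivity analyses:** missing counted as not maintained, and completers only.

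The cost is wording. The weights needed are already scheduled in 4.3.4, so no visits or subjects are added. The downside is a possibly lower reported maintenance rate.

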#### 4.3.4. Follow-Up Schedule

Follow-up visits for treatment and control patients will occur according to the following schedule: Visits at 1 week, 2 weeks, and 4 weeks ( $\pm$  3 days), and thereafter every 4 weeks ( $\pm$  2 weeks) until primary endpoint assessment at 32 weeks. In addition, 1-2 weeks after the adjustment procedure the subject will have a follow up appointment with the PI/NP.

Each follow-up visit will include:

1. Clinical assessment by PI or nurse practitioner or physician’s assistant for both the treatment group and control group (*Appendix E6: CRF6\_Control Group PI Follow Up* or *Appendix E7: CRF7\_Treatment Group PI Follow Up*)
2. Satiety and Dietary Assessment for both the treatment group and control group - limited to 30-45 minutes per session (*Appendix E8: CRF8\_Control Group Dietician Follow Up* or *Appendix E9: CRF9\_Treatment Group Dietician Follow Up*)
3. Record adverse events, device complications, concomitant medication (*Appendix E6: CRF6\_Control Group PI Follow Up* or *Appendix E7: CRF7\_Treatment Group PI Follow Up*)
4. Weight to be done by staff (patient may not speak with weighing personnel and may not disclose if they are control or treatment arm)

Control patients will exit the study at Week 32. Treatment patients will have the device explanted and will be followed for an additional 24 weeks according to the following schedule: Visits at Week 36 ( $\pm$  3 days) and thereafter every 4 weeks ( $\pm$  2 weeks) until 56 weeks. Treatment patients who undergo balloon extraction prior to 32 weeks will be followed from the time of balloon extraction an additional 24 weeks according to the following schedule: Visits at 4 Weeks post extraction ( $\pm$  3 days) and thereafter every 4 weeks ( $\pm$  2 weeks) until 24 weeks after the extraction.

These follow-up visits for the treatment group only, will include:

1. Clinical Assessment - only at the visit 4 weeks post extraction(*Appendix E7: CRF7\_Treatment Group PI Follow Up*)
2. Satiety and Dietary Assessment (*Appendix E9: CRF9\_Treatment Group Dietician Follow Up*)

A summary of required visits and procedures for subjects who do not require an unscheduled endoscopy is shown in the following table and provided in *Appendix B: Study Visits and Master Schedule*:

Assessment / Procedure	Screening Assessments	7 Days Prior to implant	Implantation	Adjustment	Explantation	Follow-Up Assessment weeks 1-32	WEEKS 36 - 56
Informed Consent	X						
Date of birth/gender	X						

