The second primary endpoint will be analyzed using the same five imputed datasets created for testing the first primary endpoint, but only the data from subjects in the active treatment group. The estimated proportion of subjects with a  $\geq 5\%$  weight loss at Week 32, along with their associated variance, from each dataset will then be combined using Rubin's method to estimate the overall proportion and its variance. This proportion and its variance will then be used to estimate the one-sided lower 97.5% confidence bound on the proportion of subjects with a  $\geq 5\%$  weight loss at Week 32. If this lower confidence bound exceeds 0.50 the second primary hypothesis will be rejected, and the Spatz3 will be deemed to have met its second primary hypothesis.

As a sensitivity analysis of each co-primary endpoint, an LOCF imputation procedure will be employed in which all missing data among subjects with at least one post-randomization body weight measurement are replaced by the last non-missing value.

Secondary analyses of the primary endpoints will be per protocol and will include subjects according to the actual treatment received and will exclude subjects who did not meet the inclusion criterion of baseline BMI  $\geq 30 \text{ kg/m}^2$  and  $< 40 \text{ kg/m}^2$ .

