#### **7.2. Sample size**

The true population mean %TBL in the control group is assumed to be 3.3% based on the Orbera and ReShape PMA studies. The standard deviation of %TBL is assumed to be approximately 6.6%, based on 6-month data from the Orbera PMA study. Based on these two assumptions, and a true population mean %TBL in the Spatz3 group of 10.34%, a total sample size of 240 subjects randomized 2:1 (160 in the Spatz3 group and 80 in the control group) will provide 80% power to demonstrate super-superiority of 4.5% TBL over the control at a one-sided significance of 2.5%. To account for a potential dropout rate of 15%, the final total sample size is 282 subjects randomized 2:1 (188 in the Spatz3 group and 94 in the control group).

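### Section 7.1.3 averages the five imputations before making a single 25% EWL responder call, which can bias the rate and loses the between-imputation variance; Section 7.1.2 pools the parallel 5% endpoint by Rubin's method

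*Combined protocol and SAP*

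**What the plan says.** Section 7.1.3 defines excess weight relative to a BMI of 25 and then determines 25% EWL response through "averaging the mean 32-week changes in body weight for each subject across the five imputations described for the primary endpoint to determine which subjects had" responded. Each subject therefore receives one call and the endpoint yields one rate. The only inferential statement is "This response rate will be compared to a performance goal of 35"%; no test, variance or confidence bound is given.

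Section 7.1.2 treats the second co-primary, 5% loss of total body weight, differently. The proportion and its variance are estimated in each of the same five datasets, and these "will then be combined using Rubin's method to estimate the overall proportion and its variance". A one-sided lower 97.5% bound is then compared with 50%. The imputation is a regression method in which baseline weight, BMI, gender, "study center, treatment group, and all non-missing body weight measurements through Week 32 will be included in the imputation model". A subject whose balloon is removed early counts as a dropout from that point.

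Section 7.1.5 adds nothing for this endpoint: "Missing data will be imputed as described above in" Section 7.1.2. Section 7.1.4 also works on an average of the five datasets, for subgroup analyses of mean %TBL.

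**The concern.** Multiple imputation draws each missing value with residual noise so that the completed data have the right spread. Averaging five draws per subject removes most of that noise. For a mean this does not alter the point estimate. For a responder rate it does, because the cut-off is non-linear: imputed subjects predicted above their cut-off are called responders too often, and those predicted below it too seldom. The net direction depends on which subjects drop out.

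There is also a loss of precision information. One set of calls gives one proportion, so the variation between imputations can no longer be estimated. An analyst following Section 7.1.3 would naturally attach an ordinary binomial SE, as though the imputed outcomes had been observed.

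At stake are the reported value and interval of one of only two secondary endpoints, one that carries a pre-set performance goal.

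**Working it through.** **Inputs from the plan (Section 7.2).** Spatz3 mean %TBL 10.34, control mean 3.3, SD 6.6, margin 4.5, 188 Spatz3 subjects, 15% dropout ("To account for a potential dropout rate of 15"%). The plan's own sample size reproduces: the excess over the margin is 10.34 - 3.3 - 4.5 = 2.54, and 160 + 80 = 240 subjects give 80.2% power at one-sided 2.5%. Dividing, 240/0.85 = 282.4, against 282 stated. The plan gives no expected rate or power for the 25% EWL endpoint.

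**Assumptions not in the plan.** The rate is that of the Spatz3 arm with n = 188; all subjects are at BMI 35; the correlation r between the last earlier weight and week-32 outcome is 0.7 to 0.9 (Section 4.3.4 schedules visits every four weeks "until primary endpoint assessment at 32 weeks"); the data are missing at random.

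**True rate.** In %TBL, the cut-off is 25 × (BMI - 25)/BMI = 25 × 10/35 = 7.14. The true rate is Φ((10.34 - 7.14)/6.6) = 0.686. The sampling SE is √(0.686 × 0.314/188) = 3.4 points.

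**Mechanism for one subject (r = 0.7).** The residual SD is 6.6 × √(1 - 0.49) = 4.71. A subject predicted at the mean, 3.20 above the cut-off, has response probability Φ(3.20/4.71) = 0.75. The average of five draws has SD 4.71/√5 = 2.11, so the averaged call is a response with probability Φ(3.20/2.11) = 0.94. A subject predicted equally far below the cut-off goes from 0.25 to 0.06.

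**Random dropout, closed form.** The averaged value of an imputed subject has SD 6.6 × √(r² + (1 - r²)/5).

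- r = 0.7: SD 5.08; rate Φ(3.20/5.08) = 0.736, which is 5.0 points above 0.686. Times 15%: about +0.7 points overall.
- r = 0.9: SD 6.08; rate 0.701, which is 1.5 points above 0.686. Times 15%: +0.2 points overall.

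**Simulation.** This used n = 188, five regression imputations with parameter draws, 15% missing and 20,000 replicates per case (Monte Carlo SE of bias below 0.03 points). Dropout depends on earlier loss through a probit slope per SD, with slope 0 meaning random and larger slopes meaning poor losers leave more often. Biases are in percentage points.

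| Slope | Averaged, r=0.7 | Averaged, r=0.9 | Rubin, r=0.7 | Rubin, r=0.9 |
|---|---|---|---|---|
| 0 | +0.76 | +0.22 | +0.01 | +0.01 |
| 0.5 | +0.02 | -0.10 | +0.01 | 0.00 |
| 1.0 | -0.66 | -0.40 | +0.05 | +0.02 |
| 1.5 | -1.10 | -0.59 | +0.10 | +0.06 |

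The binomial SE from the averaged calls, divided by the actual SD of that estimate, is 0.88-0.92 at r = 0.7 and 0.96-0.98 at r = 0.9, that is, 2-12% too small. The Rubin SE divided by its actual SD is 1.03-1.05.

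**Other BMIs.** With known parameters over BMI 30 to 39.9 and r from 0.7 to 0.9, the averaged bias is +0.1 to +0.9 points for random dropout and -1.5 to +0.8 points when dropout follows poor earlier loss.

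**Weaker prediction or more missing data.** A separate simulation with random dropout and r from 0.3 to 0.85 gave averaged biases of +0.4 to +2.0 points at 15% missing and +0.7 to +4.1 points at 30% missing. Rubin pooling gave 68.6-68.7% throughout.

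**Verdict against 35%.** With a lower 97.5% bound, both methods meet the goal in 100% of runs at the planned effect. With the true rate set at 35%, the pass rate is 1.0-2.0% after averaging and 1.9-2.2% with Rubin pooling (slopes 0, 1.0 and 1.5).

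**The case against.** The strongest reply is that nothing turns on this. The endpoint is secondary, the planned effect clears 35% under either method, and at the goal itself averaging does not inflate the false-positive rate. That stands, and it is why the point is minor.

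Second, the shift is not fixed in size or sign. It is close to zero in some cases (+0.02 at r = 0.7 and -0.10 at r = 0.9, both at slope 0.5), and it depends on r, the dropout pattern and the missing share, none of which the plan settles. Section 7.1.2 uses every available weight, so prediction will be better for late dropouts than for early ones. The plan does not say whether the 15% includes early explants, and Section 7.1.1 may take the analysed number below 188. This also stands: the figures illustrate a range and do not forecast the trial's result.

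Third, the understated SE belongs to a binomial calculation that Section 7.1.3 never specifies. That is correct, but the section specifies no alternative, and one set of calls cannot supply the missing variance component.

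Finally, Section 7.1.4 also averages, so this may be a deliberate convention for non-primary analyses. That would explain the choice without justifying averaging ahead of a threshold.

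**Conclusion.** The concern holds and is minor. Section 7.1.3 states a rule that can bias the 25% EWL response rate and that discards between-imputation variance, while Section 7.1.2 already contains the appropriate method for a responder endpoint from the same datasets.

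At BMI 35, with 15% missing and r of 0.7 to 0.9, the bias runs from about +0.8 to -1.1 points, against at most about 0.1 point with Rubin pooling and a sampling SE of 3.4 points. Weaker prediction or a larger imputed share would increase it. Confidence is high in the mechanism. The size depends on the assumed BMI, correlation, dropout pattern and missing share. The co-primary analyses are unaffected, and no change in the conclusion against 35% was found.

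**What to change.** Rewrite the analysis sentence of Section 7.1.3 so that 25% EWL response is classified within each of the five imputed datasets, the five proportions and their variances are combined by Rubin's method as in Section 7.1.2, and the resulting one-sided lower 97.5% bound is compared with 35%. Section 7.1.3 currently names no bound; the 97.5% level is carried over from Section 7.1.2 for consistency, and the sponsor should confirm it.

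The cost is a wording change. The datasets and the pooling step already exist for the second co-primary. The interval will be slightly wider, and the reported rate may move a little in either direction.

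### Both secondary endpoints are compared with performance goals without a stated test, level or confidence bound, and without a gate on the co-primaries or an order between them

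*Combined protocol and SAP*

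**What the plan says.** Section 3.2.1 lists two secondary endpoints: keeping 40% of the weight lost with the balloon six months after its removal, and losing at least 25% of excess body weight at 32 weeks.

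Section 7.1.3 is the whole analysis plan for both. The observed maintenance rate "will be compared to a performance goal of 50" per cent. For EWL response, each subject's weight change is averaged over the five imputed datasets and the subject is then classified. After that, "This response rate will be compared to a performance goal of 35" per cent.

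Section 7.1.2 treats the second co-primary, also a single-arm rate set against a goal, quite differently. It states null and alternative hypotheses, combines the imputed proportions and their variances by Rubin's method, and gives a decision rule on a one-sided lower 97.5% bound: "If this lower confidence bound exceeds 0.50 the second primary hypothesis will be rejected".

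Section 7.2 sizes the trial for the first co-primary only, "at a one-sided significance of 2.5" per cent. No section gives a level, power or sample size for a secondary endpoint, makes secondary testing conditional on the co-primaries, or describes any multiplicity adjustment.

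**The concern.** A performance goal is normally a threshold that a result either meets or misses. Section 7.1.3 names two such thresholds but does not say what counts as meeting them. Three things are left open.

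- **The criterion.** The observed rate could be enough, or a confidence bound could have to clear the goal. These differ by 14 responders out of 188 for EWL (66 against 80) and 13 for maintenance (95 against 108).
- **The gate.** Nothing says whether a secondary result may be presented as met when a co-primary has failed.
- **The order.** With two endpoints and no sequence or adjustment, either could be put forward alone, and a sequence cannot validly be chosen once the results are known.

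If these are settled after the data are seen, a secondary result reported as having met its goal could rest on evidence well short of what the plan asks of its own co-primaries.

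**Working it through.** **1. The plan's own figure.** Section 7.2 supplies the inputs. For the control mean: "The true population mean %TBL in the control group is assumed to be 3.3" per cent. For the device mean: "a true population mean %TBL in the Spatz3 group of 10.34" per cent. For the spread: "The standard deviation of %TBL is assumed to be approximately 6.6" per cent. The margin is 4.5% and allocation is 2:1.

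- Excess over the margin: 10.34 − 3.3 − 4.5 = 2.54.
- Standard error with 160 and 80 subjects: 6.6 × √(1/160 + 1/80) = 0.904.
- Power: Φ(2.54/0.904 − 1.96) = 80.2% (79.9% by noncentral t).
- Dropout: 240/0.85 = 282.4, against 282 in the plan.

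The claim that 240 subjects "will provide 80% power to demonstrate super-superiority of 4.5% TBL over the control" is reproduced. It covers the first co-primary only.

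**2. If the comparison uses the point estimate.** Let X be the number of responders among n Spatz3 subjects. The endpoint passes if X/n exceeds the goal. I take n = 188 (randomised) and n = 160 (after the planned dropout) for both endpoints; this is an assumption. Exact binomial tails when the true rate equals the goal:

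| Goal | n | Smallest passing count | Chance of passing |
|---|---|---|---|
| EWL 35% | 188 | 66 | 51.5% |
| EWL 35% | 160 | 57 | 46.4% |
| Maintenance 50% | 188 | 95 | 47.1% |
| Maintenance 50% | 160 | 81 | 46.9% |

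These are values at the boundary. For EWL with n = 188, P(X ≥ 66) falls to 7.5% at a true rate of 30% and 2.0% at 28%.

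**3. If the rule for the second co-primary is applied.** The table gives the smallest count whose one-sided lower 97.5% bound exceeds the goal. Wald and exact bounds give the same cut-offs.

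| Goal | n | Count needed | Exact type I error |
|---|---|---|---|
| EWL 35% | 188 | 80 (42.6%) | 1.9% |
| EWL 35% | 160 | 69 (43.1%) | 2.0% |
| Maintenance 50% | 188 | 108 (57.4%) | 2.4% |
| Maintenance 50% | 160 | 93 (58.1%) | 2.4% |

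With n = 188, EWL counts from 66 to 79 (35.1% to 42.0%) would pass on the point estimate but not on the bound. These counts ignore between-imputation variance, so the bound under Rubin's method could need somewhat more.

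**4. If two one-sided 2.5% tests are meant, with no gate or order.** The chance of at least one false success when both true rates equal their goals:

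- upper limit: 2 × 2.5% = 5.0%;
- independent: 1 − 0.975² = 4.9%;
- correlation 0.5 (bivariate normal): 4.5%;
- correlation 0.8: 3.9%.

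The documents give no correlation between the endpoints, hence the range.

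**5. The imputation step.** The second co-primary combines a proportion and its variance across five datasets, so between-imputation variance is kept. Section 7.1.3 averages the weights first and classifies each subject once, so that variance is lost. A binomial bound put on the averaged classification would tend to be too narrow.

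**The case against.** The strongest reply is that Section 7.1.3 makes no formal claim. It states no null hypothesis and no success rule, and the plan nowhere defines a secondary success. The comparisons may be meant as supportive description, in which case the defect is missing specification rather than error inflation. This stands in part. The figures in steps 2 and 4 follow from different readings of the word *compared*, the documents do not say which is meant, and the two sets must not be added together. But a numerical goal with no criterion still leaves the choice of reading until after the data are seen.

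A reader might infer that a secondary result could rescue a failed trial. The documents do not support this. The protocol synopsis joins the co-primaries with AND, and each has its own one-sided 97.5% bound.

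A reader might also infer that only EWL lacks a bound. Maintenance has none either, and its reference to an observed rate points at least as much to a point estimate.

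Nor is 51.5% a general false-positive rate. It applies when the true rate is exactly 35%, with 188 subjects and a point-estimate rule.

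Finally, under the plan's own assumptions the 35% to 42% zone may never matter. A 25% loss of excess weight (measured above BMI 25) is a total-weight loss of 25 × (BMI − 25)/BMI per cent. With mean 10.34, SD 6.6 and normality assumed, the expected response is about 80% at BMI 31, 69% at BMI 35 and 58% at BMI 39. This reduces the practical risk for EWL if those assumptions hold. It says nothing about maintenance.

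**Conclusion.** The concern holds for both secondary endpoints. The plan gives each a goal but no criterion for meeting it, no dependence on the co-primaries, and no order or adjustment. The co-primary conclusions are unaffected.

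The size depends on the reading. With a point-estimate comparison, the chance of passing at a true rate equal to the goal is 46% to 52% per endpoint, falling quickly below the goal. With two ungated one-sided 2.5% tests, the excess is small: at most 5.0% for at least one false success, against 2.5%.

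These figures assume 188 or 160 Spatz3 subjects in both analyses. Section 7.1.1 removes from the efficacy analysis subjects found ineligible at endoscopy, and the maintenance denominator is not stated, so actual numbers may be smaller. The point should be corrected before analysis, but it does not threaten the main result.

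**What to change.** In Section 7.1.3:

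1. State null and alternative hypotheses for each secondary endpoint and require a one-sided lower 97.5% confidence bound above the goal (50% for maintenance, 35% for EWL response), as for the second co-primary.
2. Classify EWL response within each of the five imputed datasets and obtain the bound by Rubin's method, not from averaged weights.
3. Test the secondary endpoints only if both co-primaries are met.
4. Before data are seen, fix either a testing order that stops at the first failure or Holm's procedure. The choice is the sponsor's. With a fixed order, or with Holm, the familywise error for the two secondaries is held at 2.5% one-sided. Under Holm the first step uses 2.5%/2 = 1.25%, so the bound at that step is a 98.75% bound.

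If the endpoints are meant only as description, a sentence saying so, with the goals removed, would also settle the matter.

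The cost is a few sentences, with no added patients, visits or data. In a fixed order, the later endpoint cannot be claimed if the earlier one fails. If maintenance comes first, the week-32 EWL claim must wait for the six-month post-removal data, at about week 56.
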